#### **16. c) Implementation**

All participants who fulfill eligibility criteria and who give consent for participation will be randomized by [name] into two groups.

## **17. Blinding (masking):**

Participants will be blinded to the intervention they were assigned to. Outcome assessors will be blinded as well as statisticians. The principal investigator cannot be blinded due to the difference in manipulation and application of restorative materials

## **C) Data collection, management, and analysis:**

### **18. Data Collection methods:**

For every patient, medical and dental history and caries risk assessment profile will be obtained. The examination chart will be filled in by ([name]). [name] will record telephone numbers and address of all subjects in the study as a part of the signed consent. [name] will receive a phone call at the time of the pre-determined follow-up date.

#### **Patient retention:**

The patient's phone number will be recorded in their charts and before every visit the patient will receive a reminder call by ([name] and [name]). If the patient did not answer, another appointment will be scheduled within a week.

### **19. Data management:**

All paper sheets that are concerned with the personal or outcome data will be stored in locked cabinet and in the computer at the Conservative department. The excel sheets of the patient's data will be stored in the computer of the Conservative Department- Faculty of Oral and Dental Medicine. The computer will have a password only known to [name] and [name] to prevent unauthorized access to data and double data entry.

### **20. Statistical analysis plan:**

#### **a) Statistical Methods:**

Data will be analyzed using Medcalc software, version 19 for windows (MedCalc Software Ltd, Ostend, Belgium). Categorical data will be described as frequency and percentage. Intergroup comparisons between categorical variables will be performed using the chi square test, while intragroup comparisons within each intervention will be performed using Cochran's Q test followed by pairwise multiple comparisons. A p-value less than or equal to 0.05 will be considered statistically significant and all tests will be two tailed. The statistical power of the study will be set at 80 % with 95 % confidence level.

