## **B) Study Objectives:**

### **7. Aim of the study:**

This study is conducted to evaluate the clinical performance of low-shrinkage giomer resin composite versus resin-modified glass ionomer in restoration of cervical caries lesions, using both Modified USPHS and Revised FDI criteria.

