## 12. Outcomes

Outcomes will be assessed by mouth mirror, dental explorer, standardized photographs and FDI probe according to modified USPHS criteria and Revised FDI criteria for direct and indirect restorations:

- **Primary outcomes:** All restorations will be assessed for functional, biological, and aesthetic properties using Revised FDI criteria for direct and indirect restorations. They will be given a score (clinically excellent/very good, clinically good, clinically satisfactory, clinically unsatisfactory, clinically poor).
- **Secondary outcomes:** Cost-Effectiveness Analysis

Cost-effectiveness will be assessed by calculating the Incremental Cost-Effectiveness Ratio (ICER) and the Cost per Success Ratio (CPSR). These metrics will be used to compare the cost and clinical outcomes of LS-GRC and RMGI in treating class V cavities.

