#### **b) Primary and Secondary Outcomes:**

All outcomes will be assessed after 12 months; with follow up at baseline, 6, and 12 months.

Prioritization of outcomes	Outcome	Measuring device	Measuring unit
Primary Outcome	Functional, biological, and aesthetic properties.	Revised FDI criteria for direct and indirect restorations ( Hickel R, 2022 )	Ordinal data (Scores)
Secondary Outcomes	Cost-Effectiveness Analysis	Incremental Cost-Effectiveness Ratio (ICER) and the Cost per Success Ratio (CPSR)	Currency

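### The primary outcome is a five-level ordinal FDI score, but the within-group test and the stated power belong to a binary endpoint, and no FDI property or cut-point is named for the primary comparison

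*Combined protocol and SAP*

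**What the plan says.** Section 12 states the primary outcome: "All restorations will be assessed for functional, biological, and aesthetic properties using Revised FDI criteria for direct and indirect restorations". Five ordered grades follow: "They will be given a score (clinically excellent/very good, clinically good, clinically satisfactory, clinically unsatisfactory, clinically poor". The table in section 20b gives the measuring unit as "Ordinal data (Scores".

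Section 20a supplies the tests: "Intergroup comparisons between categorical variables will be performed using the chi square test, while intragroup comparisons within each intervention will be performed using". The within-group method that it goes on to name is the one due to Cochran, given as a "Q test followed by pairwise multiple comparisons". It names no other test and no step that turns the score into two classes. It adds: "The statistical power of the study will be set at 80 % with 95 % confidence level".

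Section 14 derives that power from a two-sided Z test of two proportions. Success there means score A or B for marginal discoloration, 68.7% in the control group, with a 30-point difference. This gives 23 per group, raised to 28 for dropout.

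Two scales are in play. The aim refers to cervical restorations assessed "in restoration of cervical caries lesions, using both Modified USPHS and Revised FDI criteria", and section 12 says outcomes are judged "according to modified USPHS criteria and Revised FDI criteria for direct and indirect restorations". The primary outcome itself is given on the FDI scale only.

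FDI success appears only in the cost ratios of section 12. The ICER uses the rate of clinically excellent restorations. The CPSR text defines success first as absence of failure and then as clinically excellent.

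**The concern.** An analyst working from the plan cannot tell which variable, on which scale, decides the superiority question. The outcome table points to five ordered levels. Cochran's Q and the sample size point to two.

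- **Cochran's Q.** It compares related proportions, here over baseline, 6 and 12 months. It has no meaning on a five-level score.
- **Power.** The 80% belongs to a binary marginal-discoloration endpoint that is not declared primary and is not linked to any FDI grade.
- **Endpoint.** Three groups of FDI properties are listed together. No single property, overall score or cut-point is designated for the primary comparison.
- **Chi-square (secondary).** On five levels it gives the same result however the grades are ordered, and with 23–28 per arm its table will be sparse.

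At stake are whether the primary analysis can be reproduced from the plan, and whether the power statement says anything about it.

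**Working it through.** **1. The plan's own sample size.** Inputs from section 14: p1 = 0.687, p2 = 0.687 + 0.30 = 0.987, two-sided α = 0.05 (z = 1.96), power 80% (z = 0.8416). The mean proportion is 0.837.

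n = [1.96·√(2 × 0.837 × 0.163) + 0.8416·√(0.687 × 0.313 + 0.987 × 0.013)]² / 0.30² = (1.024 + 0.402)² / 0.09 = 22.6, so 23 per group.

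The figure reproduces, but only as a two-class comparison. Exact enumeration of the chi-square test at these rates gives power 89.8% (n = 23) and 95.2% (n = 28).

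**2. Fit of each method to the declared outcome.**

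| Item | Needs or assumes | Declared outcome |
|---|---|---|
| Cochran's Q (20a) | binary response | five levels: cannot be run |
| Chi-square (20a) | any categories | runs, ignores order |
| 80% power (14, 20a) | binary marginal discoloration | no stated link to an FDI score |

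**3. Carrying the plan's effect to five levels.** This is illustrative. The documents give no FDI distribution, so control distributions and proportional odds are assumed. The odds ratio is (0.987/0.013) / (0.687/0.313) = 75.92 / 2.195 = 34.6. Two assumed control distributions (in %, best grade first) contain 68.7% versus 98.7% at one cut: 40/28.7/20/8/3.3 (top two grades) and 68.7/25/5/1/0.3 (top grade). Simulated power, 40,000 trials per scenario:

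| Control distribution | n per arm | Five-level chi-square | Wilcoxon-Mann-Whitney | Loss (points) |
|---|---|---|---|---|
| 40/28.7/20/8/3.3 | 23 | 96.8% | 99.7% | 2.9 |
| 40/28.7/20/8/3.3 | 28 | 99.2% | 99.9% | 0.7 |
| 68.7/25/5/1/0.3 | 23 | 72.9% | 89.5% | 16.6 |
| 68.7/25/5/1/0.3 | 28 | 84.7% | 94.8% | 10.1 |

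Part of the loss comes from sparse tables rather than from ignoring order. With no true difference, chi-square rejects in only about 3–4% of trials, and about 95–100% of tables have an expected count below 5.

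**4. A smaller effect.** At an odds ratio of 4 with n = 28 and three spread distributions (30/30/20/12/8, 50/25/15/7/3, 40/28.7/20/8/3.3), power is about 42–53% for five-level chi-square and 68–78% for the rank test.

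**5. The cut-point.** For 40/28.7/20/8/3.3 at odds ratio 34.6, cumulative control rates of 40%, 68.7% and 88.7% become 95.8%, 98.7% and 99.6%. For example, at the first cut the odds are 0.667 × 34.6 = 23.1, and 23.1/24.1 = 95.8%. The gaps are 55.8, 30.0 and 10.9 points. Binary power at n = 28 is 99.9% (top grade), 95% (top two) and 36% (top three).

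**6. Sparse cells in a binary analysis.** At the planning rates the expected number of failures per arm is 28 × (0.313 + 0.013)/2 = 4.6, below 5.

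**The case against.** The best defence is that superiority rests on the between-group test, and a five-level chi-square is runnable as written. That stands. Cochran's Q is a within-arm analysis and does not decide the trial. Chi-square also does not inflate the error rate here. It can beat a rank test when the groups differ without one being uniformly better: in three assumed shifts of that kind it had 60–81% power against 7–18%. Choosing between the two is therefore an efficiency question, and for spread scores at the plan's effect the loss is trivial.

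The alternative defence is that a binary analysis is plainly intended. Then the measuring unit in section 20b is wrong and the cut-point is missing. The cost-ratio definitions do not fill the gap: they serve another outcome, and the two in the CPSR text conflict.

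A reader might infer more than the documents support:

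- **That chi-square is invalid or the sample size is miscalculated.** Neither follows. The 23 reproduces, and chi-square suits a binary endpoint fixed in advance, subject to the low expected counts.
- **That the investigators mean to pick a property or cut-point after seeing the data.** No section proposes this. The choice is simply left open.
- **That scores A and B are modified USPHS grades.** This is possible, since that scale is also applied, but no section says so.

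**Conclusion.** The point holds in this form. Two parts need no simulation: the within-group test cannot be run on the declared outcome, and the 80% power was derived for a different, binary variable. Because no FDI property, overall score or cut-point is named, the plan does not fix what the primary comparison tests.

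Chi-square against an order-based test is a secondary recommendation. Its cost is about 1–3 or 10–17 power points in the two assumed distributions that carry the plan's effect, partly through sparse tables. It is roughly 25 points for spread scores at an odds ratio of 4. The cut-point matters more: 36% to 99.9% power in one illustration. All five-level figures rest on assumed distributions and proportional odds. They show direction and range, not the power this trial will have.

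**What to change.** In section 20a, before outcome analysis, name one primary FDI endpoint at 12 months: a single property, or one overall score with the rule that derives it. Then choose one route.

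- **A, ordinal.** Compare groups with Wilcoxon-Mann-Whitney or a proportional-odds model. Replace Cochran's Q with Friedman's test and multiplicity-corrected signed-rank pairs. State that the 80% power does not apply to this test.
- **B, binary.** Fix one FDI success cut-point and state how it corresponds to scores A and B in section 14. Change the measuring unit in section 20b to binary. Keep Cochran's Q and the between-group chi-square, with an exact or mid-p test if expected counts fall below 5.

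Either way, say that the 80% power was derived for binary marginal discoloration only, and label the remaining properties and the within-group tests secondary.

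The change is wording, with no added visits or data. Route A leaves the primary test without a stated power until one is computed, and is less sensitive to differences that do not run in one direction. Route B discards the ordering. If Fisher's exact test is used under B, power at the planning rates is 80.6% (n = 23) and 83.4% (n = 28), against 89.8% and 95.2% for chi-square.

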#### **b) Primary and Secondary Outcomes:**

All outcomes will be assessed after 12 months; with follow up at baseline, 6, and 12 months.

Prioritization of outcomes	Outcome	Measuring device	Measuring unit
Primary Outcome	Functional, biological, and aesthetic properties.	Revised FDI criteria for direct and indirect restorations ( Hickel R, 2022 )	Ordinal data (Scores)
Secondary Outcomes	Cost-Effectiveness Analysis	Incremental Cost-Effectiveness Ratio (ICER) and the Cost per Success Ratio (CPSR)	Currency

**c) Handing of missing data:**

All randomized participants will be included in the primary analysis according to the intention per protocol analysis. Participants who discontinue or are lost to follow-up will be analyzed in the groups to which they were originally assigned, regardless of adherence to the intervention. No imputation will be performed for missing outcome data unless otherwise specified.

**d) Interim analyses and stopping rules:**

The study will be designed to continue until the planned sample size was reached and all follow-up completed, with no provision for early stopping. The trial will be completed according to this original protocol without any interim evaluations or modifications.

**D) Data monitoring:**

**21. Monitoring**

[name] and [name] will monitor this study, who will have full access to the results and will take the final decision to terminate the trial.

**22. Harms**

Operator [name] should inform participants about the possible harms (pain, loss of restorations, leakage, and fracture of restoration). If present, participants should contact the operator at the moment through telephone. For assessment radiograph, inspection, percussion, and vitality tests are performed; the data should be reported to the main supervisor ([name]) and managed through removal of the restorations and alleviation of pain.

**23. Audit**

In this trial auditing will be done by the main and co-supervisors ([name] & [name]) to assure quality of the research methods, restorative techniques, and interventions.

**IV. Ethics and dissemination**

**24. Research ethics approval**

Application forms for accomplishing clinical trial, checklist and informed consent of Research Ethics Committee (REC) Faculty of Oral and Dental Medicine, Cairo University will be retrieved and filled, then will be delivered for REC committee for approval, this is done to prevent any ethical problems during the study or any harms for any of the participants.

**25. Protocol amendments**

If a new protocol is used a protocol amendment will be submitted, containing a copy of the new protocol and a brief explanation about the differences between it and the previous protocols. If there is a change in the existing protocol that affects safety of subjects, investigation scope, or scientific quality of the trial an amendment containing a brief explanation about the change must be submitted. If a new author is added to accomplish the study an amendment including the investigator's data and qualifications to conduct the investigation will be submitted to prevent ghost authorship.

## **26. Informed consent**

[name] is responsible for admitting and signing the informed consents during enrollment day.

## **27. Confidentiality**

The name and the personal data of the participants will not appear on the protocol form and should be maintained secured for 10 years after the trial. This is done for protection of participants' privacy and civil rights.

## **28. Declaration of interest**

There is no conflict of interest, no funding or material supply from any parties.

## **29. Access to data**

Access to final data will be allowed to [name] and the main and co-supervisors ([name] & [name]) of the study who are not involved in assessment of the outcome.

## **30. Post-trial care**

Patients will be followed up after restoration to ensure oral hygiene measures. When there is any evidence of restoration failure, patients will be treated by immediate restoration removal and glass ionomer restoration will be placed.

## **31. Dissemination policy**

Trial results will be available in the database department and a copy of the thesis will be available at the department library and at the official site of the Egyptian Universities Libraries Consortium. Final report of the trial will be also published in international journals. The trial will be further publicized via conferences, seminars and expert meetings in Egypt and abroad.

## V. Appendices

### 32. Informed consent

## **VI. Statement of originality**

### **33. Statement of originality**

The impact of cervical caries is bidirectional on both the tooth surface and periodontal tissues, increasing the impact of both diseases on a patient's oral health status. The ability to obtain a completely isolated field, gain proper access to the lesion, restore it while fulfilling the biological, esthetic, and mechanical properties should be considered. Thus, it will eliminate the financial burden for the community in return, through long standing restorations without the need for repair or replacement (*AlQranei MS et al, 2021*).

